10.4.2.1 Missing Data

We will perform attrition analyses on whether participants and dropouts differ on key variables (severity of cannabis use disorder or CUD, as measured by the CUDIT-R) and whether variables on which they differ interact with treatments to affect outcome measures. As participants will be randomized to treatment, it is unlikely that missing data will produce biased estimates of treatment effect, as observed and unobserved covariates should theoretically be balanced across treatment groups. Larger proportions of data missing at random (MAR) or missing not at random (MNAR) could potentially bias study findings and reduce power. Should substantial proportion of cases (over 10%) for a critical independent variables and evidence of non-randomness, missing data will be incorporated using multiple imputation methods and inverse probability weighting. Results will be examined in patients who completed at least one of their randomized assigned intervention sessions as supportive analyses. First the distribution of the missing indicator variable given the observed data is modeled to derive a propensity score. Then observations are grouped on these propensity scores and an approximate Bayesian bootstrap multiple imputation is applied to each group. This has previously been identified as a fruitful method in other addiction treatment research [Witkiewitz et al., 2015, *Addiction*, "Pain as a predictor of heavy drinking and any drinking lapses in the COMBINE study and the UK Alcohol Treatment Trial"].

10.4.3 Safety Analyses

The tolerability of the RS-tDCS system will be assessed by both the Adverse Event Report frequency (which will be compared with Fisher's exact test with active and sham as categories, and the mean cumulative function (MCF) for analyzing multiple/repeated occurring AEs to subjects during the treatment period), and participant retention in the study.

10.4.4 Adherence and Retention Analyses

Compliance with the interventions will be assessed by summarizing the distributions of numbers and proportions of completed sessions by intervention group. Supportive analyses will evaluate the effects of compliance on results for the primary outcome of change in distress from baseline to end of treatment. Compliance measures will be incorporated into the primary outcome of Aim 1 (distress) analysis models to estimate the effect of compliance on the primary outcome.

10.4.5 Planned Interim Analysis

N/A

10.4.6 Exploratory Analyses

We will collect exploratory cognitive and symptomatic measures towards our ultimate objective of evaluating its effects on disease burden. Exploratory outcomes of cognitive (BICAMS, Cogstate Brief Battery) and symptoms (SymptomMScreen) measures will be evaluated in a manner similar to that described above for the primary outcome.

10.5 Sample Size

Power analyses were conducted independently for Aim 1 and Aim 2, wherein estimated effect sizes came from 2 independent manuscripts that used tDCS to measure changes in distress (Aim1) and estimated changes in cannabis use (Aim 2). In the planned study subjects will be assessed at 5 time points with the Change from V1 being used as a dependent variable (4 pieces of data per dependent measure per participant).

There is an anticipated interclass correlation coefficient (ICC) of 0.8 for the within-subjects measures. The design effect which accounts for multiple correlated observations within each subject, is estimated to be 4.2 ($DE = [1 + (5-1) 0.8]$). In a clustered setting, the sample size is $N_{\text{effective}} = nm/DE$ where n is the number of subjects required when m replications within participants are performed after accounting for the design effect (DE). The estimated number of individuals needed to detect an effect in the active RS-tDCS group is 28 for Aim 1 and 15 for Aim 2 (1-sided alpha of 0.05 and power of 80%).

CONFIDENTIAL

This material is the property of the NYU School of Medicine and Langone Medical Center. Do not disclose or use except as authorized in writing by the study sponsor
Interventional Template Version: 11 January 2019

For this study, we will utilize a 2:1 randomization based on pragmatic considerations including timeline, cost, and the added value of over recruiting to the Active group in order to have a better assessment of safety and tolerability data. In corporation this information into the total planned recruitment size, we arrived at n=42(=50 * 4.2 / 5). (28 allocated to active, 14 allocated to sham). We anticipate enrolling 52 participants which includes 10% drop out rate.

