4.2 Study Endpoints

4.2.1 Primary Study Endpoints

- Change in distress measured by Kessler Psychological Distress Scale (K10) and Positive and Negative Affect Schedule (PANAS) between baseline and treatment-end.
- Change in cannabis use measured by Timeline Followback Method Assessment (TLFB), Marijuana Craving Questionnaire (MCQ-17), Daily Sessions, Frequency, Age of Onset, and Quantity of Cannabis-Use Inventory (DFAQ-CU) and Cannabis Withdrawal Scale (CWS) between baseline and treatment-end.

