10.4.2 Analysis of the Primary and Secondary Endpoint(s)

The efficacy of RS-tDCS to effect the outcomes of each Aim 1 & 2 will be tested using linear mixed effects models. The dependent measures (K10 score, NA, percent of days of use, CWS, MCQ-17) will be nested within timepoint (Visit 1, 5, 10, 15, 20), with active/sham as fixed effects. This will be done using the Matlab function 'fitlme' with REML estimation predicting change from V1 values following each 5 session RS-tDCS interval (Matlab, R2020a, The MathWorks Inc.).

Given that the purpose of this pilot study is to develop effect sizes for a subsequent R01, we will also derive least-squares means effect sizes of our research strategy on distress, NA, percentage of days of use in 4 intervals [V1-V5; V6-V10; V11-V15; V16-V20]. The number of days that elapsed in each interval will be used as a covariate.

CONFIDENTIAL

This material is the property of the NYU School of Medicine and Langone Medical Center. Do not disclose or use except as authorized in writing by the study sponsor
Interventional Template Version: 11 January 2019

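### Section 10.5 cuts the required effective N of 50 to 42 by crediting five replicates per person, which does not establish 80% power for a single baseline-to-treatment-end change or for the treatment-by-time interaction

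*Combined protocol and SAP*

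**What the plan says.** Section 10.5 (Sample Size) plans five assessments, "with the Change from V1 being used as a dependent variable (4 pieces of data per dependent measure per participant"). It continues: "There is an anticipated interclass correlation coefficient (ICC) of 0.8 for the within-subjects measures". It then says: "The design effect which accounts for multiple correlated observations within each subject, is estimated to be 4.2", computed as 1 + (5 − 1) × 0.8. It defines the effective N as n × m / DE, and arrives at n = 50 × 4.2 / 5 = 42, split 28 active and 14 sham. It gives the numbers needed in the active group as 28 for Aim 1 (distress) and 15 for Aim 2 (cannabis use), at one-sided alpha 0.05 and 80% power. It gives no effect size, no SD and no derivation of the 50.

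Other sections describe what will be tested:

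- The Protocol Summary and section 4.2.1 define the primary endpoints as change "between baseline and treatment-end". Section 10.4.4 describes the primary distress outcome in the same way.
- Section 10.4.2 fits a linear mixed model "with REML estimation predicting change from V1 values following each 5 session RS-tDCS interval", with active/sham as fixed effects.
- Section 10.2 states the hypothesis as an interaction between treatment and time, and concludes that there is a treatment effect if that interaction is significant.

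**The concern.** A design effect of the form 1 + (m − 1) × ICC gives the precision of a mean over m equally correlated values. It lets 42 people stand in for 50 independent observations only if the quantity tested is such a mean and the treatment effect is the same at every value averaged. Neither condition fits the rest of the protocol.

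The endpoint is one change per instrument. The fifth value credited is the pre-treatment V1, which is subtracted out and carries no treatment effect. The background also argues that behavioural effects need a sustained course: section 2.1 says that one session has no meaningful effect, and section 2.2.2 reports benefit after ten or more. The change at session 5 is then hard to treat as a replicate of the change at session 20.

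At stake is the stated 80% power. It is the justification for 42 evaluable participants, and readers will use it to judge a null result. Section 10.4.2 says the trial is to supply effect sizes for a later grant, so the same sizing logic could be carried forward.

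**Working it through.** **Inputs.** ICC 0.8, m = 5, DE 4.2, effective N 50, n = 42 at 2:1, one-sided alpha 0.05 and power 80%, all from section 10.5; four change scores per person, from sections 10.5 and 10.4.2.

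**Step 1: reproduce the plan's figure.** DE = 1 + 4 × 0.8 = 4.2. n = 50 × 4.2 / 5 = 42.0. This matches. The active-arm figure agrees with it: 28 × 5 / 4.2 = 33.3, which is two thirds of 50. The step from an effect size to 50 cannot be reproduced.

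**Step 2: power as a function of effective N.** Assume that an effective N of 50 gives 80% power at one-sided 0.05, with the effect standardised by the SD of the change score. The expected test statistic at 50 is then 1.645 + 0.842 = 2.486. At another effective N with the same allocation,

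power = Φ(2.486 × √(N_eff / 50) − 1.645).

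The effect size cancels. For reference, the implied difference is d = 2.486 × √(1/33.3 + 1/16.7) = 0.746 SD.

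**Step 3: single treatment-end change (m = 1, DE = 1).** N_eff = 42. Power = Φ(2.486 × √0.84 − 1.645) = Φ(0.634) = 73.7%. A noncentral t calculation gives 73.5%. The n needed for 80% is 50.

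**Step 4: average of the four change scores (m = 4).** DE = 1 + 3r, n needed = 50 × DE / 4, and N_eff at 42 = 42 × 4 / DE, where r is the correlation between change scores.

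| r | DE | n needed | N_eff at 42 | Power at 42 |
|---|---|---|---|---|
| 0.5 | 2.5 | 31.25 | 67.2 | 89.2% |
| 0.6 | 2.8 | 35.0 | 60.0 | 86.0% |
| 0.7 | 3.1 | 38.75 | 54.2 | 82.7% |
| 0.8 | 3.4 | 42.5 | 49.4 | 79.6% |
| 0.9 | 3.7 | 46.25 | 45.4 | 76.6% |

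The r = 0.8 row replaces five by four and changes nothing else: n moves by 0.5 and power by 0.4 points. The r = 0.5 row applies if 0.8 is the ICC of raw scores with equal correlations at all five visits. Changes that share one baseline then correlate (1 − ρ) / [2(1 − ρ)] = 0.5, whatever the value of ρ.

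**Step 5: treatment-by-time interaction.** Its power depends on how the arm difference evolves over the visits and on the within-person covariance. The documents give no such profile, so no figure can be computed. Neither DE 4.2 nor DE 3.4 applies to it.

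**The case against.** The strongest reply is that the arithmetic is internally correct and that the model does use repeated values, so some replicate credit is legitimate. That stands for a time-averaged effect: if 0.8 is the correlation of the change scores and the average is the target, the plan's 80% is almost exactly right. But section 4.2.1 does not define the endpoint as an average, and section 10.2 does not test one.

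A second reply is that the 74% is built on an unstated effect size, and that 28 may be a requirement for the active arm alone. Neither changes the result: the effect size cancels, and 28 / 33.3 is the same ratio as 42 / 50. What does stand is the dependence on scale. If the effect behind 50 was standardised by the raw-score SD, and 0.8 is the raw ICC, a change has only 2 × (1 − 0.8) = 0.4 of the raw variance, and the same calculation gives about 97% for the single change. Section 10.5 names change from V1 as the dependent variable, which points to the change scale, but without an SD the question cannot be closed.

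Two facts limit the consequence. On the same reading, Aim 2 needs 15 × 5 / 4.2 = 17.9 in the active arm without replicate credit, and 28 covers it, so the shortfall concerns Aim 1. Also, 52 analysed participants would have Φ(2.486 × √1.04 − 1.645), about 81%, for the single change. That is an upper bound, because sections 4.1 and 5.6 count 52 at consent and expect 42 evaluable.

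A reader might infer two stronger points that the documents do not support. One is that using five instead of four by itself undoes the 80%; step 4 shows that it does not. The other is that 0.8 is a raw-score ICC, so that the trial needs only about 31 people and has 89% power. Section 10.5 attaches 0.8 to the within-subject measures without saying whether these are raw or change scores.

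**Conclusion.** The concern holds in a limited form. The reduction from 50 to 42 rests on averaging repeated values, and that does not establish 80% power for the treatment-end change or for the interaction. For the distress endpoint as worded, 28 versus 14 has about 74% power. This is conditional on 50 being the effective N for 80% at one-sided 0.05 and on the effect being in change-score SD units. For an average of four changes the range is about 77% to 89% over correlations of 0.9 to 0.5, so the stated 80% could be slightly high or clearly low. For the interaction, the power is unknown. This is a mismatch between the sample-size calculation and the quantity tested, in a pilot trial; it does not show that the trial is too small for its purpose.

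**What to change.** In section 10.5, name the contrast that the sample size is meant to power, and restate the power at 28 versus 14 for that contrast:

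- For the treatment-end change, give no replicate credit. Under the assumptions above, this puts about 74% in place of 80%.
- For a time-averaged change, use m = 4 with the correlation between change scores, and say that the average is the estimand.
- For the treatment-by-time interaction, compute power for that contrast under a stated time profile and covariance.

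In each case, give the effect size, the SD and its scale, the derivation of 50, and whether 0.8 refers to raw or change scores. The contrast named should agree with sections 4.2.1, 10.2 and 10.4.2. The cost is protocol wording and a slightly less favourable stated power for the treatment-end endpoint. No change in enrolment is needed.

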10.6 Measures to Minimize Bias

10.6.1 Enrollment/Randomization/Masking Procedures

In this pilot RCT, participants will be randomized 2:1 into one of two intervention groups consisting of active (Group 1) vs. sham (Group 2) tDCS paired with mindfulness meditation practice. A study team member who otherwise will not be involved in administering research procedures will randomize the device and keep the assignments in confidentiality (e.g. password protected spreadsheet).

During a sham session, the device is programmed to ramp up to the desired intensity (2.0 mA) and ramp down for the initial 60 seconds, with no current delivery during the session aside from the 60 seconds in the beginning and then again at the end of the session. These brief periods of stimulation serve to mimic the effects of a true stimulation session.

Randomization: We will stratify randomization by years of cannabis use (4 years or less vs. 5 or more years). Urn randomization will be used to balance the randomization assignment with respect to these strata. The purpose of stratification is to distribute this potential prognostic factor equally across treatment groups.

10.6.2 Evaluation of Success of Blinding

The integrity of the blind will be evaluated through a questionnaire that asks each individual 3 questions:

- 1) Do you think you are receiving active or sham tDCS?
- 2) Please write a brief sentence stating why you believe that to be true.
- 3) How confident are you (scale 1-10)?

The answers to Questions 1 & 3 will be entered into a non-parametric test of equality of proportions with confidence being a weighting variable and active or sham tDCS as a classification variable. The data from the written sentence will be used qualitatively for research presentations and provide insight into the participant experience.

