8.3.4 Remotely-Supervised tDCS sessions 2-19 (Visits 3-20)

- 20x20 minutes of active or sham tDCS with simultaneous mindfulness meditation (*20 minutes*)
- Self-report questionnaires will be administered through MyCap at sessions 5, 10, and 15 (*25 minutes*)
- AE reporting

8.3.5 tDCS Session 20 &Treatment-end Visit (Visit 21)

- Participants will complete tDCS session 20 (*20 minutes*)
- Repeat questionnaires and measures completed at baseline (*1 hour*)
- Perform the Cannabis 1 Panel Drug Test (*5 minutes*)
- Equipment return

CONFIDENTIAL

This material is the property of the NYU School of Medicine and Langone Medical Center. Do not disclose or use except as authorized in writing by the study sponsor
Interventional Template Version: 11 January 2019

[Last tDCS session and post-treatment questionnaires may be divided into two sessions +/- 3 days apart pending participant preference]

8.3.6 1, 2, and 3-month follow-up (months 2, 3, and 4, +/- 7 days) (Visits 22-24)

- Repeat questionnaires (30 minutes)
- Repeat cognitive measures and Cannabis 1 Panel Drug Test (only at 3-month follow-up) (35 minutes)
- Unblind after completing 3-month follow-up and brief blinding integrity questionnaire

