10.3 Analysis Datasets

Intent-to-Treat Analyses: All analyses will be performed on two samples: 1) the intent-to-treat sample consisting of all randomized subjects (n=52) and 2) the Per Protocol sample (individuals that completed all 20 sessions).

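### Section 10.6.2 assesses blinding only by a confidence-weighted test of equal guesses; at 28 v 14 a non-significant result would not be evidence that the blind held

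*Combined protocol and SAP*

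**What the plan says.** Section 10.6.2 opens with "The integrity of the blind will be evaluated through a questionnaire that asks each individual 3 questions". Question 1 is "Do you think you are receiving active or sham tDCS", a two-way choice with no option for not knowing. Question 2 asks for the reason, and those answers are kept for qualitative use. Question 3 asks for confidence on a 1-10 scale. Questions 1 and 3 are then "entered into a non-parametric test of equality of proportions with confidence being a weighting variable", with treatment arm as the classification variable.

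The section gives no significance level, sidedness, method of weighting, confidence interval, blinding index or rule for reading the result. The guess is collected once, at the end of follow-up: "Unblind after completing 3-month follow-up and brief blinding integrity questionnaire" (Section 8.3.6).

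Section 10.5 gives the planned arms as "28 allocated to active, 14 allocated to sham". Section 10.3 counts 52 randomized participants.

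**The concern.** The stated purpose is to evaluate whether blinding succeeded, which means showing that the two arms guess in much the same way. The only tool named tests for a difference. A significant result would suggest that the blind failed. A non-significant one could mean that the blind held, or only that 42 people are too few to tell.

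This matters because every measure among the primary endpoints in Section 4.2.1 (K10, PANAS, TLFB, MCQ-17, DFAQ-CU, CWS) is completed by the participant. The urine strip is a yes/no result that serves as secondary confirmation of the TLFB (Section 8.2.2). Participants are seeking treatment (Section 5.1), so expectancy could plausibly move these scores. Section 10.4.2 says that the pilot is meant to supply effect sizes for a later grant, so an unrecognised blinding failure could carry forward into that trial.

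**Working it through.** **Inputs from the documents.** Section 10.5: design effect 1 + (5 - 1) x 0.8 = 4.2, and 50 x 4.2 / 5 = 42, split 2:1 as 28 and 14. This reproduces. If all 52 randomized participants answer, the split is about 35 v 17. No power or error rate is stated for the blinding test.

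**Assumptions (not in the documents).** 80% of the active arm and 50% of the sham arm guess active; two-sided 0.05; in the base case, confidence uniform on 1-10 and unrelated to whether the guess is correct. The only alpha in Section 10.5 is one-sided 0.05, for efficacy, so that is shown as well.

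**Normal approximation, 28 v 14.**
- Pooled proportion = (28 x 0.8 + 14 x 0.5) / 42 = 29.4 / 42 = 0.70.
- SE under equality = sqrt(0.7 x 0.3 x (1/28 + 1/14)) = 0.150, so the observed difference must exceed 1.96 x 0.150 = 0.294.
- SE under 80% v 50% = sqrt(0.16/28 + 0.25/14) = 0.1535.
- z = (0.300 - 0.294) / 0.1535 = 0.04, so power is about 51.6% and the chance of a non-significant result about 48.4%.

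**Exact enumeration and simulation, same inputs.**

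| Test at 28 v 14, two-sided 0.05 | Non-significant |
|---|---|
| Pearson (true size 5.4-6.3%) | 47.2% |
| Confidence-weighted permutation, confidence 5-10 | 51.2% |
| Confidence-weighted permutation, confidence 1-10 | 54.6% |
| Unweighted permutation | 56.2% |
| Fisher exact | 57.2% |
| Yates | 59.1% |

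- At 35 v 17: Fisher 47.2%, weighted permutation 47.0%.
- At one-sided 0.05, 28 v 14: Pearson 36.6%, weighted permutation 45.1%, Fisher 50.1%.

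**If confidence tracks correctness.** With the weighted permutation test at 28 v 14, the non-significant share is about 20% when correct guessers score 3-10 and incorrect guessers 1-8. It is about 8% at 4-10 v 1-7, and about 2-3% at 5-10 v 1-6.

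**If confidence is treated as a number of cases.** For scores uniform on 1-10, the mean is 5.5 and the mean square 38.5. The assumed variance is therefore too small by a factor of 38.5 / 5.5 = 7. The test statistic then has a standard deviation of about sqrt(7) = 2.65 under an intact blind, and 1.96 / 2.65 = 0.74 corresponds to about 46% false rejections. Simulation gives about 47%. At 80% v 50% this version is non-significant in about 15% of trials.

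**Precision.** At 28 v 14 the 95% half-width for the difference is 1.96 x 0.1535 = 0.30. At 35 v 17 it is 1.96 x sqrt(0.16/35 + 0.25/17) = 0.27.

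**Would a margin help?** Take a truly intact blind with 50-70% guessing active in both arms at 28 v 14, and require the 95% Wald interval to lie inside the margin. The rule is met in about 0% of trials at 20 points, 0-9% at 30 points and 41-54% at 40 points.

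**The case against.** A reader might infer that the plan declares the blind intact whenever the test fails to reject, and so would report a clearly broken blind as intact in about 55% of trials. The documents do not support that. Section 10.6.2 names a test and stops; it never says how a non-significant result will be read, and it also collects reasons for the guess.

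Nor is 55% a property of the procedure as written. It needs a valid variance, which the plan does not specify, and it needs confidence to carry no information about correctness. In a badly broken blind, correct guessers may well be more confident, and the weighted test is then much more sensitive. The assumed guess rates and the two-sided level are also not in the documents. At one-sided 0.05, at 35 v 17, or with Pearson's test, a description of more often than not is wrong or doubtful.

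It can also be said that this is a pilot and that the guess enters no efficacy estimate, analysis population or decision.

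All of this stands, and it limits the size that can be claimed. It does not rescue the method. Under every version considered the error rates are unstated, and no version turns a non-significant test of equality into evidence that the arms guess alike.

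**Conclusion.** The point holds in a limited form. The only quantitative assessment of blinding is a weighted test of equality, with no estimate, interval or index, and at the planned size its non-significance would be uninformative about success. Under 80% v 50%, two-sided 0.05, 28 v 14 and confidence unrelated to correctness, valid tests are non-significant in about 47-59% of trials. The figure is about 47% by Fisher or weighted permutation at 35 v 17, and about 37-50% at one-sided 0.05 with 28 v 14. It drops to about 2-21% if confidence clearly tracks correctness. It drops to about 15% under case-count weighting, at the price of about 47% false alarms.

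These figures illustrate how far the answer depends on unstated inputs; they do not predict what this trial will report. The consequence is for how an active-sham difference on self-reported outcomes is interpreted, not for the efficacy test itself. The change should be made.

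**What to change.** In Section 10.6.2, replace the weighted equality test as the main summary by:
- the proportion guessing active in each arm;
- the between-arm difference with a 95% CI;
- an arm-specific blinding index (Bang) with its CI.

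Report the confidence scores (question 3) descriptively by arm and guess, not as weights. State that a non-significant p-value will not be reported as evidence that blinding succeeded.

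Do not add a pass/fail margin. At this size, margins of 20 or 30 points would almost never be met even by an intact blind, and a margin of 40 points would accept the 30-point gap used above as an example of failure.

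The cost is wording only, with the same questionnaire and data. The downside is that intervals will be wide, about 30 points either side at 28 v 14, so the usual conclusion will be that blinding success is not established.
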